5.1 POTENTIAL RISKS

As with any experimental procedure, there may be adverse events or side effects that are currently unknown, and certain of these unknown risks could be permanent, severe or life threatening. Every attempt will be taken to minimize these risks.

5.1.1 *Risks of Sodium Nitrite Inhalation Solution:*

The first-in-man clinical study of nebulized sodium nitrite Inhalation Solution, Study AIR001-CS01, was a dose escalation study designed to identify the dose limiting toxicity, the maximum tolerated dose, and the pharmacokinetics of nebulized sodium nitrite administered. The most important safety finding was a decline in systolic and diastolic blood pressure at the highest dose tested, 176 mg. Dose-dependent asymptomatic increases in heart rate were noted at all doses, although at doses up to and including the maximum tolerated dose of 125 mg, the heart rate changes were well tolerated. Increase in heart rate was not always associated with a change in blood pressure. Significant levels of methemoglobin, or changes in pulmonary function, were not observed. Methemoglobin levels increased at the highest doses administered, but remained less than 3.5% in all subjects(12).

As with any drug product administered via inhalation, it is possible that susceptible individuals, such as those with unrecognized asthma, will develop bronchospasm upon exposure to inhaled sodium nitrite solution. There were no changes in pulmonary function noted in AIR001-CS01, which excluded subjects with asthma or abnormal baseline pulmonary function tests.

In Study AIR001-CS02, inhaled nitrite was generally well tolerated under hypoxic conditions at doses up to and including 113 mg. Additionally, a sustained reduction in hypoxia-induced pulmonary hypertension was demonstrated, suggesting that safely delivered doses of nebulized sodium nitrite result in clinically significant vasodilatation, presumably through a mechanism of intrapulmonary reduction of nitrite to NO. In this study, the significant treatment related adverse event was a decrease in blood pressure. The magnitude of the change in blood pressure from the hypoxic baseline was less than from the normoxic baseline, suggesting that hypoxia itself has an effect on BP.

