The Hope Pharmaceuticals package insert includes the following warnings and precautions: hypotension, methemoglobin formation, risk for interaction with carbon monoxide (in the setting of smoke inhalation), use in the setting of known anemia (causing further decreased oxygen carrying capacity in the setting of methemoglobinemia), G6PD Deficiency, and use with PDE5 inhibitors and diuretics. Adverse reactions listed include syncope, hypotension, tachycardia, palpitations, dysrhythmia, methemoglobinemia, headache, dizziness, blurred vision, seizures, confusion, coma, nausea, vomiting, abdominal pain, tachypnea, dyspnea, anxiety, diaphoresis,

lightheadedness, injection site tingling, cyanosis, acidosis, fatigue, weakness, urticaria, generalized body numbness and tingling. Note that these reactions were reported with intravenous formulation of sodium nitrite being used to treat life-threatening cyanide poisoning, the total dose of nitrite given is 3-6 fold higher than in our study, and that the intravenous route may have more abrupt onset of effects. These adverse reactions are manifestations of systemic hypoperfusion or severe methemoglobinemia. The severe hypotension, methemoglobinemia, cardiac dysrhythmias and coma were reported in patients without life-threatening cyanide poisoning that were treated with intravenous doses less than twice those recommended for treatment of cyanide poisoning.

5.1.2 Risks of Blood Drawing:

The amount of blood to be drawn over the course of this research study could be a maximum of 5 tablespoons. To minimize the risks of blood tests, a licensed technician or registered nurse will draw blood. Common risks include temporary discomfort, bruising which may last for several days, redness, swelling, lower hemoglobin level. Infrequent risks include a subject may feel lightheaded or faint when blood is drawn. This is usually due to nervousness and is not usually serious. Rare risks include infection, and bleeding.

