***Stopping Rule:**

Two distinct scenarios in which subjects must be removed from the study are anticipated.

First, the subject experiences a CF respiratory exacerbation marked by a persistent drop in FEV₁ >15% that is not temporally associated with nebulized sodium nitrite administration. The drop in FEV₁ would be seen on the first set of spirometry at a visit, prior to dosing of nebulized sodium nitrite for that day. In this case, subjects will be removed from the study and referred to their pulmonologist for treatment of the CF respiratory exacerbation.

- Drop in FEV₁ >15% on the first set of spirometry, prior to drug administration, on any study visit when compared with baseline spirometry collected at screening.

In the second scenario, nebulized sodium nitrite is associated with a dose-dependent intolerance that will be seen at the dose escalation visit 2, or after receiving the first dose of drug on visit 1. Specific intolerances of concern are acute bronchospasm, hypotension or methemoglobinemia. In this case, if any one of the below occurs at the 45 mg dose, subject will be removed from the study; if any occur at the 90 mg dose, the subject will return to the previously tolerated dose of 45 mg.

- Decrease in FEV₁ by >15% between measurements on an individual study visit.
- A decrease in systolic BP > 40 mmHg drop from pre-dose baseline or to <80mmHg and symptomatic
- SaO₂ drop below 88% and symptomatic or SaO₂ desaturation > 5% from baseline and symptomatic
- A single occurrence of venous methemoglobin level >5%
- Any serious adverse event thought to be possibly related to the study treatment

The Investigator will prepare a detailed written summary of serious, unexpected, and treatment related adverse events, and will compare, and contrast the event with prior events. The detailed written summary will be provided to the DSMB and the IRB.

In addition, the DSMB Report addressed the following information will be submitted to the IRB at the time of continuing review annually or more often as required:

- A list of the research personnel who participated in the data and safety monitoring.
- The frequency of monitoring that took place during the renewal intervals and/or the dates that data and safety monitoring was conducted.
- A summary of cumulative data related to unanticipated problems (including adverse events) including a determination of causality and whether the risk to benefit assessment has changed.

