5.5.4 Frequency of Monitoring

The Investigator will review subject safety data as it generated. The Investigator and the research staff will meet on a quarterly interval to re-evaluate study goals, subject recruitment, data coding and retention, documentation and identification of adverse events, complaints and confidentiality of subjects. There will be an evaluation of the progress of the research study, including assessments of data quality, time lines, participant recruitment, accrual, and retention. The Investigator will also review the outcome and adverse event data to determine whether there is any change to the anticipated benefit-to-risk ratio of study participation and whether the study should continue as originally designed or should it be re-evaluated and changed.

The iDSMB is expected to meet at least two times a year at the call of the Chairperson to review the progression of the study including patient enrollment, protocol compliance, and adverse event reports. An emergency meeting of the iDSMB may be called at any time by the Chair should participant safety questions or other unanticipated problems arise.

5.5.5 Adverse Event Reporting:

The study investigators will be responsible for detecting, documenting and reporting events that meet the following definition of an adverse event as defined below:

Adverse event. Any untoward medical occurrence in a clinical study; regardless of the causal relationship of the event with the investigational drug or study treatment(s).

Associated with the use of the investigational drug or study treatment(s). There is a reasonable possibility that the adverse event may have been caused by the investigational drug or study treatment(s).

Disability. A substantial disruption of a person's ability to conduct normal life functions.

Life-threatening adverse event. Any adverse event that places the patient or subject, in the view of the investigator, at immediate risk of death from the event as it occurred (i.e., does not include an adverse event that, had it actually occurred in a more severe form, might have caused death).

Serious adverse event. Any adverse event occurring at any dose that results in any of the following outcomes: death, a life-threatening adverse event, inpatient hospitalization or prolongation of existing hospitalization, a persistent or significant disability/incapacity, or a congenital anomaly/birth defect.

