Hospitalization shall include any initial admission (even if less than 24 hours) to a healthcare facility as a result of a precipitating clinical adverse event; to include transfer within the hospital to an intensive care unit. Hospitalization or prolongation of hospitalization in the absence of a precipitating, clinical adverse event (e.g., for a preexisting condition not associated with a new adverse event or with a worsening of the preexisting condition; admission for a protocol-specified procedure) is not, in itself, a serious adverse event.

Unexpected adverse event. Any adverse event, the frequency, specificity or severity of which is not consistent with the risk information described in the clinical protocol(s) or elsewhere in the current IND application, as amended.

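### Prompt notice to the DSMB of a serious drug-related event depends on that event being judged unexpected, and the protocol's own risk text allows the three named intolerances to be judged expected

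*Combined protocol and SAP*

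**What the plan says.** **Event-level notice.** Under the stopping rule in section 5.5.2, "The Investigator will prepare a detailed written summary of serious, unexpected, and treatment related adverse events", and "The detailed written summary will be provided to the DSMB and the IRB". No time limit is attached. Sections 5.6.1.1 (FDA) and 5.6.2 (IRB) use the same three conditions, numbered and joined by a conjunction. They do have limits: 15 calendar days for the FDA, and 10 calendar days for the IRB, or 24 hours if the event is fatal or life-threatening.

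**Toxicities of interest.** The same stopping rule says "Specific intolerances of concern are acute bronchospasm, hypotension or methemoglobinemia".

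**Meaning of unexpected.** Section 5.5.5 defines it as "Any adverse event, the frequency, specificity or severity of which is not consistent with the risk information described in the clinical protocol(s". Risk information held in the IND application counts as well.

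**Risk information.** Section 5.1.1 says of the intravenous package insert: "Adverse reactions listed include syncope, hypotension, tachycardia, palpitations, dysrhythmia, methemoglobinemia, headache, dizziness, blurred vision, seizures, confusion, coma", among others. It also says of the inhaled route that "it is possible that susceptible individuals, such as those with unrecognized asthma, will develop bronchospasm upon exposure to inhaled sodium nitrite solution".

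**Periodic review.** Section 5.5.4 says "The iDSMB is expected to meet at least two times a year at the call of the Chairperson". Adverse event reports are among the items reviewed, and the Chair may convene an emergency meeting. Section 5.2.1 nevertheless counts uninterrupted monitoring by the board among the protections against drug risk.

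**The concern.** The objective of this trial is safety, it is open label, and an investigator-sponsor runs it. The board is the independent check. A filter on unexpectedness is usual for expedited regulatory reports. Applied to the board, it means that a serious, drug-related case of a toxicity the trial is watching for can lose its prompt route because the toxicity was foreseen.

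The protocol does not treat expectedness as relevant when it acts on the individual subject. Any serious event thought possibly related is an intolerance criterion in sections 2.6 and 5.5.2, with no such test. It also leaves the judgement loosely assigned: section 5.5.6.4 tells the investigator-sponsor to decide adverse-event status, causality and seriousness, but does not mention expectedness. What is at stake is how many further subjects start dosing before anyone independent has seen the case.

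**Working it through.** The plan gives no figure on this point to reproduce. The check has two parts.

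**1. Can a serious, related case be classed as expected?** The test is frequency, specificity or severity against the risk text, so the risk text decides.

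| Intolerance | Text supporting expected | Text supporting unexpected |
|---|---|---|
| Hypotension | Named as a prior finding (2.5). Symptomatic hypotension and tachycardia in 2 of 6 at 176 mg, and symptomatic orthostasis in 2 of 3 at 120 mg, both inhaled (1.3.3). Severe hypotension after intravenous use (5.1.1). | Those inhaled doses exceed the 45 and 90 mg used here. In the later patient studies, one withdrawal for asymptomatic hypotension (1.3.3). |
| Methemoglobinemia | Named as a prior finding (2.5). Severe form after intravenous use (5.1.1). | Inhaled levels stayed below 3.5% in the first-in-man study (5.1.1). |
| Bronchospasm | Described as possible in susceptible people (5.1.1). | No severity or frequency given. No pulmonary function change in the first-in-man study, which excluded asthma and abnormal baseline tests (5.1.1). |

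For each of the three, a classification of expected can be defended from the protocol. The case is strongest for hypotension and weakest for bronchospasm. The protocol does not settle any of them.

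**2. How long is the delay, and how many subjects start dosing in it?**

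Inputs: N = 35 (2.2.1); two meetings a year, the stated minimum (5.5.4). Assumptions: meetings evenly spaced; event equally likely at any time between meetings; even accrual over 12 to 24 months, because the protocol gives no accrual period.

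- Longest delay = 52 / 2 = 26 weeks (6 months).
- Mean delay = 26 / 2 = 13 weeks (3 months).
- Subjects starting in the delay = N × delay / accrual period.

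| Accrual (assumed) | Mean delay, 3 months | Longest delay, 6 months |
|---|---|---|
| 12 months | 35 × 3/12 = 8.75 | 35 × 6/12 = 17.5 |
| 24 months | 35 × 3/24 = 4.4 | 35 × 6/24 = 8.75 |

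So about 4 to 9 on average, and 9 to 18 at worst. With the 10-day limit proposed below, the corresponding upper bound is 35 × 10/365 = 0.96 for 12-month accrual and 35 × 10/730 = 0.48 for 24-month accrual, that is, about one subject or fewer.

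**The case against.** **The board is not blind.** A reader might infer that only serious, unexpected and related events ever reach it. The plan does not say that. Section 5.5.1 has the board look at accumulating data, section 5.5.3 covers adverse events and withdrawals, and the adverse event reports reviewed under section 5.5.4 carry no expectedness filter. This stands. The gap is in prompt notice, not in what the board eventually sees.

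**A listed term is not automatically expected.** A reader might infer that bronchospasm, hypotension and methemoglobinemia all count as expected because section 5.1.1 names them. The definition turns on frequency, specificity or severity, and section 5.1.1 attributes the insert's reactions to intravenous treatment of cyanide poisoning at total doses 3 to 6 fold higher. A serious methemoglobinemia at 45 or 90 mg could well be unexpected in severity. This also stands, and it makes the point conditional on a judgement.

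**Other routes may exist.** Section 5.5.2 commits to IRB reporting under an institutional manual that is not reproduced, so it cannot be said that no event-level report would be made to anyone. That manual governs reporting to the IRB, however, and the protocol does not present it as a route to the board.

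**The three conditions might be separate categories.** The punctuation in section 5.5.2 permits that reading. The numbered triggers in sections 5.6.1.1 and 5.6.2, and the reference in 5.5.2 to comparing a single event with earlier ones, favour requiring all three together. If separate categories were intended, the text should say so.

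**The event may be rare.** Section 1.3.3 reports no treatment-related serious events in more than 30 patients with pulmonary arterial hypertension treated for as long as 12 months. That lowers the chance that the gap matters, but those were not patients with cystic fibrosis, and airway reactivity in that disease is the stated reason for this trial.

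**Conclusion.** The point holds in a limited form. Prompt notice to the board depends on an expectedness judgement that the protocol leaves open for exactly the three toxicities it singles out, and even an event that passes the filter has no deadline. A related serious event judged expected waits for a periodic review. The Chair's power to call an emergency meeting does not close the gap, because no rule tells the Chair that such an event has occurred. Nor does this arrangement deliver the uninterrupted monitoring listed in section 5.2.1.

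The delay is about 13 weeks on average and up to 26. The counts of 4 to 9 subjects on average and 9 to 18 at worst rest on evenly spaced meetings at the stated minimum frequency and on an assumed 12 to 24 months of even accrual. More frequent meetings or slower accrual would reduce them; uneven spacing or faster accrual could increase them. The 9 to 18 range should not be read as typical, since it requires the event to fall just after a meeting.

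This is a cheap improvement to a reporting rule. It does not show that the trial is unsafe as designed.

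**What to change.** In section 5.5.2, separate the board's criterion from the IRB's and drop the expectedness condition for the board. For example: *Each serious adverse event considered at least possibly related to study treatment, whether expected or not, will be sent to the iDSMB Chair within 10 calendar days of the investigator learning of it, or within 24 hours if it is fatal or life-threatening.* These are the limits section 5.6.2 already applies to the IRB.

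Keep the relatedness condition. Forwarding every serious event would also send the Chair unrelated admissions, such as those for CF exacerbations, and the argument here does not call for that. Leave the FDA and IRB criteria, the dosing rules and the subject-level stopping criteria as they are.

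The cost is one sentence and a few extra forwarded reports, with no added visits or procedures. The protocol gives no rate for related serious events. At an assumed 1% to 10% of subjects with one such event each, the total would be 35 × 0.01 = 0.35 to 35 × 0.10 = 3.5 reports over the whole trial.

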5.5.3 Parameters to be Monitored

The following progress will be monitored throughout the course of the research to ensure the safety of subjects as well as the integrity and confidentiality of their data.

- An evaluation of the progress of the research study, including subject recruitment and retention, and an assessment of the timeliness and quality of the data.
- A review of collected data (including adverse events, unanticipated problems, and subject withdrawals) to determine whether there is a change to the anticipated benefit-to-risk assessment of study participation and whether the study should continue as originally designed, should be changed, or should be terminated.
- An assessment of external factors or relevant information (eg. Pertinent scientific literature reports or therapeutic development, results of related studies) that may have an impact on the safety and study participants or the ethics of the research study.
- A review of study procedures designed to protect the privacy of the research subjects and the confidentiality of their research data.

5.5.4 Frequency of Monitoring

The Investigator will review subject safety data as it generated. The Investigator and the research staff will meet on a quarterly interval to re-evaluate study goals, subject recruitment, data coding and retention, documentation and identification of adverse events, complaints and confidentiality of subjects. There will be an evaluation of the progress of the research study, including assessments of data quality, time lines, participant recruitment, accrual, and retention. The Investigator will also review the outcome and adverse event data to determine whether there is any change to the anticipated benefit-to-risk ratio of study participation and whether the study should continue as originally designed or should it be re-evaluated and changed.

The iDSMB is expected to meet at least two times a year at the call of the Chairperson to review the progression of the study including patient enrollment, protocol compliance, and adverse event reports. An emergency meeting of the iDSMB may be called at any time by the Chair should participant safety questions or other unanticipated problems arise.

5.5.5 Adverse Event Reporting:

The study investigators will be responsible for detecting, documenting and reporting events that meet the following definition of an adverse event as defined below:

Adverse event. Any untoward medical occurrence in a clinical study; regardless of the causal relationship of the event with the investigational drug or study treatment(s).

Associated with the use of the investigational drug or study treatment(s). There is a reasonable possibility that the adverse event may have been caused by the investigational drug or study treatment(s).

Disability. A substantial disruption of a person's ability to conduct normal life functions.

Life-threatening adverse event. Any adverse event that places the patient or subject, in the view of the investigator, at immediate risk of death from the event as it occurred (i.e., does not include an adverse event that, had it actually occurred in a more severe form, might have caused death).

Serious adverse event. Any adverse event occurring at any dose that results in any of the following outcomes: death, a life-threatening adverse event, inpatient hospitalization or prolongation of existing hospitalization, a persistent or significant disability/incapacity, or a congenital anomaly/birth defect.

Hospitalization shall include any initial admission (even if less than 24 hours) to a healthcare facility as a result of a precipitating clinical adverse event; to include transfer within the hospital to an intensive care unit. Hospitalization or prolongation of hospitalization in the absence of a precipitating, clinical adverse event (e.g., for a preexisting condition not associated with a new adverse event or with a worsening of the preexisting condition; admission for a protocol-specified procedure) is not, in itself, a serious adverse event.

Unexpected adverse event. Any adverse event, the frequency, specificity or severity of which is not consistent with the risk information described in the clinical protocol(s) or elsewhere in the current IND application, as amended.

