Exclusion Criteria:	
1. Inability to provide consent2. Use of supplemental oxygen or non-invasive ventilatory support3. FEV₁ < 40%4. Awaiting lung transplantation5. Pregnancy or unwilling to comply with birth control during the intervention period6. History of glucose-6-phosphate dehydrogenase (G6PD) deficiency or any contraindication to receiving methylene blue7. Hospitalization within the past 4 weeks prior to enrollment8. Subject requires additional antibiotics or steroids within the past 4 weeks prior to enrollment9. Change in maintenance CF therapies in the past 4 weeks prior to enrollment10. Baseline systemic hypotension (systolic BP < 90 mm Hg)11. History of orthostatic hypotension or syncope12. Chronic kidney disease (creatinine > 2.5 or requiring dialysis)13. Severe anemia (Hgb <9 gm/dL in the last six months)14. History of portal hypertension or chronic liver disease, including hepatitis B and/or hepatitis C (with evidence of recent infection and/or active virus replication), defined as moderate to severe hepatic impairment (Child-Pugh Class B-C)15. History of abusing alcohol or illicit drugs within 28 days prior to study16. Severe pulmonary hypertension (mean PA pressure > 25)17. Use of sildenafil or other pulmonary vasodilator18. History of any organ transplantation19. Participation in another interventional trial in the previous 28 days
Study Endpoints:	
Primary endpoint:
 
The primary safety and efficacy endpoint is FEV₁. A sustained decrease in FEV₁ of >15% will be considered intolerable.
 
Secondary endpoints include exhaled NO (FE_{NO}), sputum nitrite concentration, quantitative bacterial cultures, percutaneous methemoglobin levels, blood pressure, and subject symptoms as measured by the CF Questionnaire-R.

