2.3 STUDY TREATMENT

The study treatment will be delivery of nebulized sodium nitrite by nebulization at the dose of 45 or 90 mg.

Table 1 Dose Limiting Toxicity Criteria

Sign or Symptom	Moderate	Severe ¹
Bronchospasm/ wheezing	Symptomatic but not requiring therapy	Symptomatic and requiring therapy
Decrease in FEV_1	>15%	>25%
SBP ²	Systolic \geq 20 mm Hg drop from pre-dose baseline AND symptomatic, or SBP <80 mm Hg AND symptomatic	Systolic > 30 mm Hg drop from pre- dose baseline AND symptomatic or requiring fluid replacement or other therapy
Dyspnea	Causes more discomfort (than a mild, easily tolerated AE) and interrupts the subject's usual daily activities	Incapacitating and causes considerable interference with the subject's usual daily activities
Cough	Causes more discomfort (than a mild, easily tolerated AE) and interrupts the subject's usual daily activities	Incapacitating and causes considerable interference with the subject's usual daily activities
Hypoxia ³	$SaO_2 > 5\%$ drop from baseline AND symptomatic	$SaO_2 \geq 10\%$ drop from baseline or $SaO_2 < 88\%$ AND symptomatic

Percutaneous methemoglobin ^{4,5}	>5% and <7%	≥7%
Other drug-related signs or symptoms ⁶	Causes more discomfort (than a mild, easily tolerated AE) and interrupts the subject's usual daily activities OR CTCAE v.4 ⁶ Grade 2 toxicity	Incapacitating and causes considerable interference with the subject's usual daily activities OR CTCAE v.4 ⁶ Grade 3 or 4 toxicity

AE = adverse event; CTCAE = Common Toxicity Criteria for Adverse Events; DLT = dose limiting toxicity; SBP = systolic blood pressure; SaO₂ = oxygen saturation (hemoglobin)

1. Severe DLT seen in any subject which is deemed to be study drug-related will preclude further dosing with nebulized sodium nitrite for that subject.
2. Moderate or Severe SBP without symptoms will be continuously monitored with BP measurements every 5 minutes. Symptomatic refers to dizziness or fainting. Discontinuation of further dosing or dose escalation will be based upon follow up blood pressure measurements, subject symptoms and physician-investigator discretion (see Stopping Rules).
3. Moderate or Severe SaO₂ without symptoms will be continuously monitored and recorded every 5 minutes until return of saturation > 92%.

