2.6 STOPPING RULES

Two distinct scenarios in which subjects must be removed from the study are anticipated.

First, the subject experiences a CF respiratory exacerbation marked by a persistent drop in FEV1 >15% that is not temporally associated with nebulized sodium nitrite administration. The drop in FEV1 would be seen on the first set of spirometry at a visit, prior to dosing of nebulized sodium nitrite for that day. In this case, subjects will be removed from the study and referred to their pulmonologist for treatment of the CF respiratory exacerbation.

Drop in FEV1 >15% on the first set of spirometry, prior to drug administration, on any study visit when compared with baseline spirometry collected at screening.

In the second scenario, nebulized sodium nitrite is associated with a dose-dependent intolerance that will be seen at the dose escalation visit 2, or after receiving the first dose of drug on visit 1. Specific intolerances of concern are acute bronchospasm, hypotension or methemoglobinemia. In this case, if any one of the below occurs at the 45 mg dose, subject will be removed from the study; if any occur at the 90 mg dose, the subject will return to the previously tolerated dose of 45 mg.

Specific criteria for dose-dependent intolerance are:

Decrease in FEV1 by >15% between measurements on an individual study visit.

A decrease in systolic BP > 40 mmHg drop from pre-dose baseline or to <80mmHg and symptomatic.

SaO₂ drop below 88% and symptomatic or SaO₂ desaturation > 5% from baseline and symptomatic

A single occurrence of venous methemoglobin level >5%

Any serious adverse event thought to be possibly related to the study treatment

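### The serious-event definition in 5.5.5 omits important medical events treated without admission, leaving a gap in expedited reporting, the visit 2 escalation check and the serious-event count

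*Combined protocol and SAP*

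**What the plan says.** Section 5.5.5 makes an event serious by outcome: "Any adverse event occurring at any dose that results in any of the following outcomes: death, a life-threatening adverse event, inpatient hospitalization", and then "or prolongation of existing hospitalization, a persistent or significant disability/incapacity, or a congenital anomaly/birth defect". That gives five kinds of outcome, and no other section adds to them.

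Two neighbouring definitions set the edges of the list. A life-threatening event must place the subject, in the investigator's view, "at immediate risk of death from the event as it occurred"; an event that could have killed only in a worse form is expressly left out. For admission, "Hospitalization shall include any initial admission (even if less than 24 hours) to a healthcare facility".

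Seriousness is then a condition in several rules:

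- 2.2.1, visit 2: escalation requires no serious event in the first week, plus steady blood pressure and FEV1 on arrival.
- 2.6, 2.14.2 and 5.5.2: one stopping item is "Any serious adverse event thought to be possibly related to the study treatment".
- 5.5.2: "The Investigator will prepare a detailed written summary of serious, unexpected, and treatment related adverse events", sent to the DSMB and the IRB.
- 5.6.1.1 and 5.6.2: FDA and IRB reports for events that are related, serious and unexpected.

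Table 1 in 2.3 grades toxicity on a different scale. Its Severe entry for bronchospasm, for example, is "Symptomatic and requiring therapy". The safety analysis in 2.15.2 lists a summary of SAEs but spells the abbreviation out as severe adverse events.

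**The concern.** The trial's objective is safety, and the toxicities it expects are of a kind that can be treated and reversed on site. Visits are outpatient (2.11). Observed doses are given in research units with two hours of monitoring, and a subject who does not tolerate the first dose is observed until stable and sent home (2.2.1). Excluding people with "any contraindication to receiving methylene blue" shows that treatment of methemoglobinemia is foreseen.

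Under a list tied to death, admission and lasting harm, whether such an event counts as serious can depend on where it was treated and not on what it was. At stake are how quickly the FDA, the IRB and the DSMB learn of a related and unexpected event, whether a first-week event at home is seen by the escalation check, and what a reported serious-event count means.

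**Working it through.** The plan gives no figure on this point, so the check sets the definition against the rules that use it and the rules that do not.

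**Step 1. Table 1 Severe rows against the five serious outcomes, with no admission and no life-threatening judgment.**

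| Severe row | Criterion (short form) | Meets a listed outcome by itself? |
|---|---|---|
| Bronchospasm/wheezing | symptoms and need for treatment | No |
| FEV1 | fall >25% | No |
| Systolic BP | fall >30 mm Hg with symptoms, or fluid/other treatment needed | No |
| Hypoxia | SaO2 fall of 10% or more, or <88% with symptoms | No |
| Methemoglobin | 7% or more | No |
| Dyspnea | incapacitating | Possibly (incapacity) |
| Cough | incapacitating | Possibly (incapacity) |
| Other drug-related | incapacitating, or CTCAE grade 3 or 4 | Possibly (incapacity) |

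8 rows − 3 possible = 5 rows that meet no listed outcome on their own terms.

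**Step 2. What protects the affected subject without the word serious.** A drug-related Severe toxicity ends that subject's dosing (Table 1, footnote 1; also 2.5). A single venous methemoglobin above 5% does the same (footnote 5). Sections 2.6, 2.14.2 and 5.5.2 list FEV1, systolic pressure, SaO2 and methemoglobin criteria beside the serious-event item. For observed doses, subject-level protection is therefore largely duplicated.

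**Step 3. What is left to the rules worded on seriousness.**

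- *Reporting.* The reports in 5.6.1.1 and 5.6.2 need three conditions: related, serious and unexpected. I read the summary in 5.5.2 the same way. Section 5.1.1 describes bronchospasm, hypotension and methemoglobin formation as risks, so many such events would be expected. But 5.5.5 also counts an event as unexpected when its frequency, specificity or severity departs from the described risk. Section 5.1.1 reports methemoglobin below 3.5% in all subjects of the first inhaled study; Table 1 Severe begins at 7%, and 7 / 3.5 = 2, at least twice that ceiling. The same section lists severe effects of the intravenous product, so expectedness is arguable. Under the present definition, the question is not reached for an event treated without admission and not judged life-threatening or disabling.
- *Escalation at visit 2.* Doses between visits 1 and 2 are taken at home. The gate in 2.2.1 looks for serious events and for blood pressure and FEV1 on arrival. It does not cite Table 1. The second stopping scenario in 2.6 is framed around visits 1 and 2, and several criteria need measurements that are not scheduled at home. A faint at home in week one, without admission and with normal readings at visit 2, can pass the gate as worded.
- *Later subjects.* The stopping rules are all subject-level. The DSMB is scheduled at least twice a year (5.5.4), while 2.2.1 runs dosing from day 0 to day 28, so a full course fits between scheduled meetings. The written summary that would arrive sooner is restricted to serious events.
- *Count.* Read literally, 2.15.2 tabulates severe events under the label SAE and names no separate table of events meeting 5.5.5.

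**The case against.** The other side has considerable force. Four stronger readings are tempting, and the documents do not support them.

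- *A reader might infer that these events escape every safeguard.* They do not. The triggers in step 2 need no serious classification, and the investigator may withdraw a subject at any time. A home event may also be caught by the Table 1 row for other drug-related events, and 2.11 schedules an adverse-event assessment and a tolerability determination at visit 2.
- *A reader might infer that such an event is always non-serious.* The life-threatening criterion needs no admission and rests on the investigator's view; 5.6.1.2 and 5.6.2 give it its own faster route if the event is also unexpected. Any admission counts, however short.
- *A reader might infer that the definition alone would leave the trial with no expedited reports.* The unexpected condition would exclude many of these events even under a wider definition, because they are listed risks.
- *A reader might size the gap from 2.15.1.* Its 5–10% expectation applied to 35 subjects gives 35 × 0.05 = 1.75 to 35 × 0.10 = 3.5. But that rate concerns discontinuation for an FEV1 fall above 15%, which is Table 1's Moderate threshold; Severe is above 25%. Nothing says those subjects would need treatment, so the figure does not measure this gap.

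Nor is concealment shown. Section 2.15.2 tabulates all events, events by maximum severity, drug-related events and events leading to withdrawal. The DSMB reviews adverse event reports generally and can be convened in an emergency. Institutional IRB policies, which are referred to but not reproduced, may require more.

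These points narrow the consequence. They do not supply the missing category, make the expedited reports independent of seriousness, or tie the visit 2 gate to Table 1.

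**Conclusion.** The point holds as a gap in reporting, in the escalation check and in counting; it does not show a general loss of subject protection. A related event treated without admission, and not judged life-threatening or disabling, is non-serious under 5.5.5. It therefore falls outside the rules worded on seriousness, including the serious-event stopping item, although the separate criteria largely cover dosing of that subject.

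Its size can be stated only structurally: five of eight Severe rows meet no serious outcome by themselves. The documents give no basis for a number of subjects or of missed reports.

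The conclusion assumes that the definition is applied as written, and that institutional IRB policies not reproduced here do not already close the reporting part. It rests on the protocol's own wording and not on any outside regulation. It should be corrected: the trial's objective is safety and the change is small.

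**What to change.** 1. Add to the list in 5.5.5: *or an important medical event that, in medical judgment, may jeopardize the subject or require intervention to prevent one of these outcomes*.
2. State that the clause applies to the written summary in 5.5.2 and to the FDA and IRB reports in 5.6, with the related and unexpected conditions unchanged.
3. Correct 2.15.2 so that serious events (as defined in 5.5.5) and severe events (by grade) are defined and tabulated separately.
4. The wider definition changes what the serious-event items capture. The sponsor must therefore reconcile the visit 2 gate in 2.2.1, Table 1 and its footnotes in 2.3, and the lists in 2.6, 2.14.2 and 5.5.2. These already disagree: for an event at 90 mg, 2.6 returns the subject to 45 mg, while the Table 1 footnotes end dosing for a drug-related Severe toxicity or a venous methemoglobin above 5%. No clinical rule is proposed here.

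The cost is one clause, two cross-references and one corrected table description. The downside is a few more serious-event forms and possibly a less favourable serious-event count.
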